#### 1.0 Research Design

#### 1.1 Purpose/Specific Aims

To determine feasibility and explore the relevance of modulating the gut microbiota by an Investigational New Drug NBT-NM108 as an early treatment for suspected or confirmed symptomatic COVID-19 patients.

#### A. Objectives

To determine the safety, feasibility, and effectiveness of using NBT-NM108 to modulate the gut microbiota in patients who have suspected or confirmed COVID-19

#### B. Hypotheses / Research Question(s)

Overgrowing opportunistic pathogens in gut microbiome may be one of the major driver for developing more severe complications in patients who have COVID-19. Our overall hypothesis is that supplementing COVID-19 patients with a combination of fermentable dietary fibers of diverse physicochemical structures provides an additional energy source that will promote a select group of acetate and butyrate producers in the gut. Akin to the tall trees as the foundation species for a closed forest, this group of bacteria may work as the "Foundation Guild" in the gut microbiota that change the gut environment and suppress the overgrowing opportunistic pathogens, which may reduce the severity of COVID-19-related illness.

#### 1.2 Research Significance

The world is facing the COVID-19 pandemic induced by the virus SARS-CoV-2 [1]. Some COVID-19 patients with pre-existing conditions have a significantly higher risk of developing a severe form of the disease, higher hospitalization rate and increased mortality compared with the average patient population [2, 3]. Immunopathology induced by cytokine storm and sepsis from opportunistic pathogens are among the most common causes of mortality in COVID-19 patients, particularly those with those with pre-existing conditions [4].

A dysbiotic gut microbiota may be a major driver of the more severe clinical outcome in COVID-19 patients[5]. The dysbiotic gut microbiota has significantly higher abundance of opportunistic pathogens and toxin producers, including endotoxin-producing pathogens and producers of hydrogen sulfide [6]. These opportunistic pathogens increase the antigen load and sustain a higher level of inflammation [7]. If gut barrier function is impaired, these pathogens may translocate to internal organs and induce sepsis [8]. Viral infection to the intestinal epithelial cells can impair the gut barrier and increase gut permeability [9]. Thus, patients with dysbiotic gut microbiome may have a higher risk of developing a more severe form of the infection with catastrophic clinical outcomes due to: 1) a higher level of baseline inflammation with a greater risk of developing immunopathology; 2) more abundant opportunistic pathogens in the gut with a higher risk of developing sepsis; and 3) more severe gut barrier impairment if viral gut infection and hyperglycemia co-occur.

This randomized controlled trial will use a high fermentable dietary fiber formula (NBT-NM108, Notitia Biotechnologies, Wilmington, DE) as perturbation to improve the gut microbial ecosystem of patients who have COVID-19-like symptoms. We hypothesize that the predominance of a select group of acetate and butyrate producers supported by the additional fiber as an energy source may work as the "Foundation Guild" in the gut microbiota that can suppress the overgrowing opportunistic pathogens. Akin to the tall trees of a forest, members of the Foundation Guild maintain a healthier gut microbiota structure by producing short-chain fatty acids (SCFAs), particularly acetate and butyrate, that can make the gut environment inhibitory to opportunistic pathogens by: 1) acidifying the gut; 2) producing antimicrobials; and 3) taking up more available niches. Our recent clinical trial showed that a high-fiber diet effectively promoted the Foundation Guild in T2DM patients and shifted the gut microbiota structure that led to better clinical outcomes [6]. Studies in mice and chickens with various respiratory virus infections showed that acetate and butyrate from fermentable fibers significantly reduced disease severity and boosted antiviral immunity [10-15].

# 1.3 Research Design and Methods

#### A. Research Procedures

Protocol Title: COVGUT20

**RECRUITMENT.** We are recruiting patients who have mild to moderate COVID-19-like symptoms and pending/positive SARS-CoV-2 PCR test results. Prospective participants will be identified using two strategies: 1) online advertisements via Google, Facebook and Twitter will be sent to residents of mainland US. A link to the landing page of the study will also be distributed to family physicians and doctors in the USF and Rutgers University medical schools and facilities, and patient organizations via email, text and messaging apps for them to share with their patients and networks. Webinar will also be hosted to general public and information about this clinical trial will be posted. 2) individuals who have been tested positive for COVID-19 using services from Vault Health company, at the Carol & Frank Morsani Center for Advanced Healthcare drive-through testing center at University of South Florida (USF) or at Rutgers University medical schools. An email (Appendix 25) will be sent to potential participant with a link to the landing page of the study.

ELIGIBILITY SCREENING PART 1. For online recruitment, individuals who are interested in participating in the study will access the landing page of the study (Appendix 19) via the online advertisements (Appendix 20) or a link shared by their family physicians, Vault Health, USF or Rutgers University. The landing page will provide an overview of the study and a brief description of requirements for research participants. Study candidates will provide their email addresses to access an online self-administered preliminary screening survey (Appendix 22). At the completion of the survey the study candidates will be informed whether they may be eligible for the study, and if so they will be instructed to schedule a virtual informed consent interview with the research team using 10To8 or phone calls. For female study candidates who are of child-bearing age (16-49 years), they will receive a pregnancy test kit (Rapid Detection Pregnancy Test, Clearblue, Geneva, Switzerland), perform the test at home and report their pregnancy status to the research team on Castor (Appendix 6) during the informed consent interview. For recruitment from Vault Health company, at the Carol & Frank Morsani Center for Advanced Healthcare drive-through testing center at University of South Florida (USF) or at Rutgers University medical schools. individuals who has COVID-19 related symptoms and has been tested positive for COVID-19 will be contacted by Vault Health or research staff in USF/Rutgers University. An email/phone call containing a brief description of the study and a link to the landing page will be sent to the potential participants. If the study candidate is interested in the study, they will provide their email addresses on the landing page. And the following procedure will be the same as described in section for online recruitment.

INFORMED CONSENT AND ELIGIBILITY SCREENING PART 2. The informed consent process will be conducted via Castor's eConsent video call module. At the beginning of the call, the study coordinator will confirm that the study candidates continue to experience the COVID-19-like symptoms reported in the preliminary screening survey, thereafter the study coordinator will explain the rationale, aim, expected outcomes and significance of the research, the experimental procedures, what is required from the participants, and the benefits and risks associated with the study. Electronic informed consent will be obtained during the interview prior to further eligibility screening (Appendices 3 and 4). A consent for health information release (Appendix 3) will also be obtained during informed consent procedure. After the study candidates sign the electronic informed consent documents, the study coordinator will ask some additional questions regarding their medical history and other conditions to establish eligibility (Appendix 4). In the case of study candidates who are recruited online, they will also be asked to provide electronic proofs of a positive/pending COVID-19 test (Appendix 24) and a negative pregnancy test result (if appropriate; Appendix 6) during the interview. This consent and eligibility screening interview will take a maximum of 60 minutes to complete.

**ENROLLMENT.** The study physicians will review all screening data and determine if the study candidates are suitable for home isolation and confirm enrollment.

**RANDOMIZATION AND ALLOCATION CONCEALMENT.** Enrolled participants will be randomized to the control or treatment group at a 1:1 ratio, using randomization via a dynamic minimization to minimize imbalance between groups over factors including COVID-19-like illness severity (mild vs moderate), the use of COVID-19 vaccination or other treatments that may reduce severity such as monoclonal antibody treatment vs. not used, age (≤60 vs >60 years) and gender (male vs female) [16]. When imbalance is detected, the new patient will be allocated with probability 0.7 vs 0.3. When the treatment assignments are at balance, the patient will be allocated with probability 0.5 vs 0.5. The randomization will be performed

via a closed source app written by one of the Co-PI. The investigator who uses the app will only know the allocation result, i.e., control or treatment group, of the new patient.

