All participants will evaluate objective and subjective symptoms, adverse events and medication changes twice a day (in the morning around 8 am and 2 h after dinner around 8 pm using the last 12 h as the recall period) and record fasting blood glucose if participant has T2DM (after at least 8 h of overnight fasting) and consumption of NBT-NM108 (treatment group) or water (control group) once a day from Day 1 to Day 28 or until they recover from COVID-19-like illness (whichever is later) and then once a week until Day 56 (i.e. in the mornings of Days 35, 42, 49 and 56). Participants will also report symptoms, fasting blood glucose if participant has T2DM and medication changes on the day that they recover from COVID-19like illness (if before Day 56). For measurement of body temperature (oral), oxygen saturation level, pulse rate and respiratory rate and fasting blood glucose if participant has T2DM, participants will be provided with devices and instructions to take the measurements; for the remaining subjective symptoms, participants will be asked to evaluate the severity of each symptom using categorical options of "none", "mild", "moderate", and "severe" or the severity of the symptoms as directed. Participants will be asked to record these data and any adverse events in the participant booklet (Appendices 8.1 and 8.2) and report to the research team on Castor (Appendices 9-11). For participants who are hospitalized during the study, they will stop collecting data themselves during hospitalization but body temperature (oral), pulse rate, respiratory rate, oxygen saturation level, fasting blood glucose if participant has T2DM, respiratory support and other data related to the clinical progress of COVID-19-like illness will be extracted from their medical records at the hospital. If these patients are discharged on or before Day 56, they will collect data on objective and subjective symptoms and medication changes twice a day and fasting blood glucose if

Protocol Title: COVGUT20

participant has T2DM once a day after they are discharged until they recover from COVID-19-like illness and once a week thereafter until Day 56.

Medical history and regular medications will be extracted from the primary care medical records. If participants are hospitalized during the study, clinical data related to COVID-19-like illness will be extracted from the hospital medical records.

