## 1.5 Sample Size Justification

We will enroll a total of 100 participants who have COVID-19-like symptoms and have positive/pending PCR-based COVID-19 test results. These individuals will be randomized into the control and treatment group in a 1:1 ratio (i.e. 50 participants/group). With the assumption of a positivity rate of 40-50% in symptomatic participants in the USF Carol & Frank Morsani Center for Advanced Healthcare drive-through testing center, we expect to have at least 20 confirmed COVID-19 cases in each group. We used the micropower R-package [27], in which the weighted Jaccard distance matrix was simulated based on within-group distance variance (mean and standard deviation) of data from 36 T2DM patients (unpublished data) to estimate the required sample size. Using the simulated matrices, the PERMANOVA powers are calculated for varying effect sizes ( $\omega^2$ ) and sample sizes. Our results show that 16 subjects per group afford 80% power to an  $\omega^2$  of 0.0106 which correspond to the difference ( $\omega^2$ =0.0120) between the control and treatment group with a similar high-fiber intervention in the T2DM patients (unpublished data). We therefore aim to recruit 20 confirmed COVID-19 cases in each group to allow for potential dropouts and/or incomplete sample/data sets from the participants.

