# C. Feasibility

There are over 2,000 new COVID-19 cases every day in Florida. Around 100 individuals attend the USF Carol & Frank Morsani Center for Advanced Healthcare drive-through testing center for COVID-19 testing each day and among the confirmed cases the prevalence of diabetes is 12%. We therefore consider this patient flow sufficient for recruiting the targeted number of subjects in the specified duration.

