To analyze the clinical data, Aalen's additive survival model will be used to test whether the impact of covarites on the cumulative hazard is time-dependent [35]. If the covariates do not vary with time, cox proportional hazards model will be subsequently used to adjust for age, gender, race/ethnicity, baseline COVID-19 severity, and whether the participant has taken treatments that may reduce COVID-19 severity (vaccination and monoclonal antibody treatment) as covariates. Survival analysis Kaplan-Meyer curves and log-rank test will be used to estimate and compare the risk of death and the risk of recovery, as a function of time, in participants with COVID-19-like symptoms [36, 37]. To compare the time to hospitalization, the time to recovery, the time to complete resolution of subjective symptoms, and the time to complete resolution of objective symptoms between treatment groups, we will use competing risks survival analysis (treating death or self-reported illness severity at Days 1, 14, 28 and 56 as a competing risk) [36, 38], use survival analysis without competing risk, and explore joint survival analysis and Bayesian survival model [39]. Specifically, cumulative incidence functions will be estimated and tested using Gray's test [40]. The Fine-and-Gray subdistribution hazard regression analysis [38] will be used to further adjust for age, gender, race/ethnicity, baseline COVID-19 severity, and whether the participant has taken treatments that may reduce COVID-19 severity (vaccination and monoclonal antibody treatment) as covariates. Proportion of participants who are "alive and not admitted to the hospital", proportions of participants who visit the emergency room at Days 1, 14, 28 and 56, have complete resolution of objective symptoms, have complete resolution of subjective symptoms and have complete resolution of subjective symptoms except cough and fatigue at Days 1, 14, 28 and 56 will be compared between groups using separate logistic regression analysis at each time point. Time for participants to have complete resolution of objective symptoms, complete resolution of subjective symptoms and complete resolution of subjective symptoms except cough and fatigue will be compared between groups using competing risks survival analysis described previously, treating death or self-reported illness severity at Days 1, 14, 28 and 56 as a competing risk [36, 38]. To compare the longitudinally (repeatedly) measured illness severity based on the Ordinal Scale for Clinical Improvement from the World Health Organization, body temperature (oral), oxygen saturation level, pulse rate, respiratory rate and fasting blood glucose between treatment groups, accounting for the effect of death, reported adverse event, or other appropirate competing risk, we will compare the treatment effect using the method of joint survival and longitudinal data analysis [41, 42], where each of the clinical outcomes (e.g., illness severity, body temperature (oral), and oxygen saturation level, etc.) will be modeled using linear mixed models, and death, reported adverse event, or other appropirate competing risk will be modelled using Weibull proportional hazards model [43]. Age, gender, race/ethnicity, baseline COVID-19 severity, and whether the participant has taken treatments that may reduce COVID-19 severity (vaccination and monoclonal antibody treatment) will be controlled as covariates in these statistical analyses, where appropriate. Within-group changes of main outcomes between groups will be modeled as change from pre- to post-treatment using ANOVA and modeled as the post-treatment value as the change itself with the pretreatment value entered as covariate using ANCOVA [44]. Lastly, alternative statistical methods will be explored to quantify the underlying differences between groups with respect to a time-to-event end point, robust methods include calculating ratio/difference of t-Year Survival Rates, ratio/difference of percentiles of survival functions, and ratio/differenceof restricted mean survival times or restricted mean time lost [45]. Statistical analyses described above will be conducted for both intent-to-treat dataset and per-protocal dataset. For each test of an outcome, we define the statistical significance by p<0.05. The false discovery rate [46] will be applied for multiple testing, where appropriate. Sensitivity analysis using multiple imputation methods [47] will be performed to handle the missing data. Other

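### T2DM is neither a minimization factor nor a model covariate, although fasting glucose is compared only among the roughly 12 participants expected to have it; a minor gap that is cheap to close

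*Protocol*

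**What the plan says.** **Allocation.** Protocol section 1.3 A assigns participants 1:1 "using randomization via a dynamic minimization to minimize imbalance between groups over factors including COVID-19-like illness severity (mild vs moderate"). The other factors named are "the use of COVID-19 vaccination or other treatments that may reduce severity such as monoclonal antibody treatment vs. not used", age (cut at 60 years) and gender. When the groups are out of balance, the probabilities are 0.7 and 0.3. Section 1.5 says "We will enroll a total of 100 participants who have COVID-19-like symptoms and have positive/pending PCR-based COVID-19 test results", to be "randomized into the control and treatment group in a 1:1 ratio (i.e. 50 participants/group").

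**Covariates.** Protocol section 6.1 and the SAP (Clinical Data Analysis) use the same list. The Cox and Fine-Gray models "adjust for age, gender, race/ethnicity, baseline COVID-19 severity, and whether the participant has taken treatments that may reduce COVID-19 severity", the last item meaning vaccination and monoclonal antibodies. The same variables are used in the longitudinal models. T2DM and other pre-existing conditions are in neither list.

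**Role of pre-existing conditions.** Section 1.2 states: "Some COVID-19 patients with pre-existing conditions have a significantly higher risk of developing a severe form of the disease, higher hospitalization rate", and adds increased mortality. Medical history is asked for in the screening survey and interview (sections 1.3 A and 1.9 A), before allocation. In addition, "Medical history and regular medications will be extracted from the primary care medical records".

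**Glucose.** Fasting blood glucose is a secondary outcome (section 1.3 D). It is measured only in participants with T2DM (sections 1.3 A and B) and compared between groups (section 6.1 and SAP). For expected numbers, section 4.3 C offers only that "among the confirmed cases the prevalence of diabetes is 12" per cent.

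**The concern.** T2DM status decides who enters the glucose comparison, yet nothing in the allocation keeps the two arms of that subset similar in size. With about a dozen people, an uneven split is a realistic outcome and directly widens the confidence interval.

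Separately, the Protocol's rationale treats pre-existing conditions as raising risk, and the information is in hand before allocation. If such a condition also slows recovery, leaving it out of the time-to-event models gives up some power. In the vital-sign models it leaves some explainable variation in the error term. At stake is avoidable imprecision in secondary outcomes, not the validity of the randomization.

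**Working it through.** **The plan's own figures.** The only power statement (section 1.5) is for PERMANOVA on the microbiota outcome. It cannot be reproduced, because the distance data behind it are unpublished, and it has no bearing here. No power is stated for glucose or any clinical outcome.

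**Size of the glucose subset.** Applying 12% to everyone: 0.12 × 100 = 12. Among the 40 confirmed cases (20 per group) that the plan expects at minimum: 0.12 × 40 = 4.8.

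**Chance of an uneven split.** With 12 T2DM participants among 100 and 50 per arm, the number X in one arm is hypergeometric:

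P(X = k) = C(12,k) × C(88,50−k) / C(100,50), doubled over the two arms.

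- 8-4 or worse: 35.7%
- 9-3 or worse: 12.1%
- 10-2 or worse: 2.8%

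If the number with T2DM also varies around 12, the chance of 2:1 or worse is 28% and of 3:1 or worse 9.5%. The second figure is below 12.1% because exactly 12 people can split 3:1 precisely, while neighbouring totals such as 11 or 13 need a more extreme split to reach it.

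**Cost of an uneven split.** The variance of the difference in means is proportional to 1/n1 + 1/n2. Power is from the noncentral t distribution, 10 degrees of freedom, two-sided 0.05 (sidedness is not stated in the plan), for a single summary value per person.

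| Split | 1/n1 + 1/n2 | Variance against 6-6 | Power at 1 SD | Detectable with 80% power |
|---|---|---|---|---|
| 6-6 | 0.333 | 1.00 | 35% | 1.80 SD |
| 9-3 | 0.444 | 1.33 | 27% | 2.07 SD |
| 10-2 | 0.600 | 1.80 | 22% | 2.41 SD |

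**What a fifth factor buys.** The minimization was simulated with probability 0.7 and 4,000 runs per setting. Assumed prevalences were 40% for moderate illness, 40% for vaccination or treatment, 25% for age over 60 and 50% for gender. T2DM was set at 12%, either unrelated to age or 27% above and 7% at or below 60.

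- Four factors as planned: 2:1 or worse 27.5%; 3:1 or worse 8.8% to 9.2%; mean absolute difference 2.5 people.
- T2DM added: 2:1 or worse 13.7% to 14.5%; 3:1 or worse 3.1% to 3.3% (simulation error about 0.3 points); mean absolute difference 1.8.

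The planned factors therefore do almost nothing for T2DM balance, even when T2DM is related to age.

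**What a covariate buys in the Cox models.** The next simulation used 100 participants, the same biased coin, a treatment hazard ratio of 1.7 for resolution, the four planned factors in the model and 1,500 runs per setting. Prevalence and hazard ratio of the condition are assumptions.

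| Prevalence | Condition HR | Power without | Power with | Gain (points) |
|---|---|---|---|---|
| 40% | 0.5 | 63.1% | 68.4% | 5.3 |
| 25% | 0.5 | 64.7% | 71.3% | 6.6 |
| 12% | 0.5 | 68.3% | 72.7% | 4.4 |
| 25–40% | 0.65 | about 69–70% | about 72–73% | about 3 |

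A second set of 2,000 runs per setting, assuming a 14-day median, gave gains of about 3 to 6 points at hazard ratios of 0.5 to 0.65, and 0.5 to 1.5 points at 0.8. With no treatment effect, rejection rates were 5.3% with the term and 5.1% without in one setting, and 6.4% both ways in another. The term itself adds no type I error.

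**Effect estimate.** The true log hazard ratio is ln 1.7 = 0.53. The planned model averaged 0.51 to 0.55 and the model with the extra term 0.55 to 0.57.

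**Logistic models.** At 50% control response, treatment odds ratio 3.3, condition odds ratio 2 to 4 and prevalence 12% to 40%, the covariate changed power by about −1 to +2 points.

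**The case against.** A reader might infer that the Protocol makes pre-existing conditions the main driver of severe outcome, or the most prognostic baseline factor, and then ignores them. The text does not support that. Section 1.2 says that some such patients are at higher risk; what it names as a possible major driver is a dysbiotic gut microbiota. Nothing ranks comorbidity above age, severity or vaccination.

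A reader might also infer that the planned hazard ratio is materially biased toward 1. The simulated averages do not show this: the planned model brackets the true value, and the fuller model is not clearly closer. Nor does chance imbalance inflate type I error in a randomized comparison.

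Other objections carry weight:

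- The trial is exploratory, with microbiota composition as its primary outcome, so no stated clinical power is undermined.
- Section 1.2 speaks of severe disease, hospitalization and death. The Cox gain concerns symptom resolution, for which the documents do not say that comorbidity is prognostic. Entry is also limited to mild or moderate illness managed at home. The gain is conditional and could sit at the low end.
- The 12% is diabetes of unspecified type among confirmed cases at one Florida center, whereas recruitment is national and includes pending tests.
- Glucose is limited more by subset size than by the split.

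It can also be said that neither list is strictly closed: the minimization factors are introduced as examples, and the covariates apply as judged suitable. This helps less. An allocation program needs a definite list, and the covariates are spelled out twice without T2DM.

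**Conclusion.** The point holds as a minor one. T2DM is absent from both lists, although it is known before allocation and alone determines who contributes to a secondary outcome. If about 12 participants have it, there is a 12% chance of a 9-3 or worse split and a 3% chance of 10-2 or worse. Adding T2DM to the minimization reduces splits of 3:1 or worse from about 9% to 3 to 4%, but does not make the glucose comparison informative: about 35% power for a 1-SD difference is the best case at that size.

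For the time-to-event outcomes, a covariate is worth about 1 to 7 points of power over assumed prevalences of 12% to 40% and condition hazard ratios of 0.5 to 0.8. These inputs, the treatment hazard ratio of 1.7, the factor prevalences, and the use of 12% for all 100 participants are assumptions, not document figures. The glucose power is for a single-summary t-test, not the planned joint model.

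**What to change.** 1. In Protocol section 1.3 A, add T2DM (yes/no) as a fifth minimization factor. Use T2DM itself: a pooled item for T2DM or any other condition would not balance T2DM within the glucose subset.
2. In Protocol section 6.1 and the SAP, add baseline T2DM, or a pre-existing-condition indicator with its qualifying conditions listed in advance and taken from the screening history, as a covariate. Put it in the time-to-resolution and time-to-recovery models and the vital-sign mixed models. It cannot help the glucose model, where everyone has T2DM. The simulated gain gives no reason to change the logistic models.
3. State that the glucose comparison is descriptive, reported as an estimate with its interval and the number per arm.

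If allocation is already complete, item 1 falls away; make the covariate change before outcomes are analysed by arm, and keep item 3.

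The cost is one field in the allocation program and one model term, both from data already collected. The downside is slightly looser balance on the other four factors and one degree of freedom.

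### The trial is sized on confirmed COVID-19 cases, but infection status is not a named minimization factor, covariate or analysis set, which costs precision and interpretability

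*Protocol*

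**What the plan says.** **Who is enrolled.** Protocol 1.3 A (Recruitment) seeks "patients who have mild to moderate COVID-19-like symptoms and pending/positive SARS-CoV-2 PCR test results". At the consent interview for online recruits, "they will also be asked to provide electronic proofs of a positive/pending COVID-19 test". Section 1.5 repeats the rule: "We will enroll a total of 100 participants who have COVID-19-like symptoms and have positive/pending PCR-based COVID-19 test results".

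**What the size rests on.** Participants are "randomized into the control and treatment group in a 1:1 ratio (i.e. 50 participants/group". From an assumed positivity of 40-50% among symptomatic attendees at one drive-through center, section 1.5 concludes: "we expect to have at least 20 confirmed COVID-19 cases in each group". It gives 16 per group as the number for 80% power and 20 as the target that allows for dropout and incomplete samples.

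**What is balanced.** Section 1.3 A (Randomization) names "factors including COVID-19-like illness severity (mild vs moderate), the use of COVID-19 vaccination or other treatments that may reduce severity", followed by age and gender. Allocation is 0.7/0.3 when imbalance is detected and 0.5/0.5 otherwise.

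**What is adjusted for.** Protocol 6.1 and the SAP (Clinical Data Analysis) list "age, gender, race/ethnicity, baseline COVID-19 severity, and whether the participant has taken treatments that may reduce COVID-19 severity". Both run the analyses on an intent-to-treat and a per-protocol dataset. PERMANOVA is given no covariates. MaAsLin2 may adjust for confounders, which are not named.

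**What is recorded.** The data points in 1.3 B do not list the final result of a pending test. Section 5.1 allows COVID-19 laboratory data to be retrieved from medical records.

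**The concern.** Section 1.5 treats the confirmed case as the unit that gives the trial its power. After that section the variable drops out of the plan: it is not named at allocation, in the models or in the definition of any analysis set.

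Infected and uninfected people with similar symptoms can be expected to differ in time to resolution and in risk of hospitalization. Baseline severity does not stand in for infection, because section 4.1 C grades COVID-19-like symptoms and signs that an uninfected person can also have.

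Two things are at stake. First, if the infected share differs between arms by g, and infected and uninfected participants differ by Δ on an outcome, the unadjusted arm difference in that trial shifts by g × Δ. A 20-point gap shifts it by 0.20 × Δ. Second, without a confirmed-case analysis the plan never makes the comparison for which the sample size was calculated.

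**Working it through.** **Inputs.** N = 100, 50 per arm, positivity 40-50%, 20 confirmed expected per arm and 16 needed for power (all Protocol 1.5). Allocation probabilities 0.7/0.3 (1.3 A). The documents do not give the share who enter already positive, so it is varied below as an assumption.

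**1. The plan's own figure.** 50 × 0.40 = 20 and 50 × 0.50 = 25. The 20 per group reproduces as the expected count at the low end of the range. It is not a minimum. With confirmed cases in each arm as Binomial(50, p), and the one-arm probability squared for both arms:

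| p | Both arms ≥ 20 | Both arms ≥ 16 |
|---|---|---|
| 0.40 | 0.5535² = 31% | 0.9045² = 82% |
| 0.45 | 0.8026² = 64% | 0.9780² = 96% |
| 0.50 | 0.9405² = 88% | 0.9967² = 99% |

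The 16-per-group, 80% power figure cannot be recomputed, because it rests on unpublished distance data.

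**2. Chance gap in infected share.** Let K of the 100 be infected. If allocation is unrelated to infection, the number X in one arm is hypergeometric. The gap in counts is 2X − K, so the SD of the gap in share is (2/50) × √[50 × (K/100) × (1 − K/100) × 50/99]. For K = 40 this is 0.04 × √6.06 = 9.8 points.

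| K | SD of gap (points) | Pr(gap ≥ 20 points) | Pr(smaller arm < 20) | Pr(smaller arm < 16) |
|---|---|---|---|---|
| 40 | 9.8 | 6.6% | 84% | 6.6% |
| 45 | 10.0 | 4.4% | 23% | 0.5% |
| 50 | 10.1 | 7.1% | 3% | 0.01% |
| 60 | 9.8 | 6.6% | about 0 | about 0 |
| 70 | 9.2 | 4.9% | 0 | 0 |

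Odd and even K give different tails because the gap moves in steps of two cases. At K = 70, an arm below 20 is impossible, since the other arm would need more than 50.

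**3. Does minimizing on positive versus pending help?** The planned 0.7/0.3 scheme was simulated (4,000 trials per scenario) with and without entry status as a fifth factor. Pending tests were assumed 40% positive, and the other factors unrelated to infection.

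| Already positive at entry (assumed) | Expected infected | Arms differ by ≥ 10 cases: without factor | With factor |
|---|---|---|---|
| 0% | 40 | 5.9% | 5.4% |
| 25% | 55 | 6.6% | 4.2% |
| 50% | 70 | 5.9% | 2.0% |
| 75% | 85 | 2.1% | 0.6% |

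Ten cases in arms of 50 is the same 20-point gap as in step 2. When everyone is pending, the factor is constant and does nothing real. When many enter positive it helps, but the shortfall of step 1 has then gone.

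**The case against.** **Randomization already balances infection on average.** This stands. Unadjusted tests remain valid and the imbalance is due to chance. A reader might infer a biased treatment comparison; the documents do not support that.

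**The infected share may be well above 40-50%.** This also stands. That figure describes attendees at one center. Sections 1.3 A, 4.1 A and 4.1 B also describe recruiting people who have already tested positive, through the testing company and, in 1.3 A, the two universities. Sections 1.9 A and 4.1 B still describe screening from test appointments, so the mix is unknown. It is therefore tempting, but unsupported, to say that about half the trial has another illness or that an arm will fall below 20 with 84% probability. The 84% needs exactly 40 infected, hence almost nobody positive at entry, and counts every split except 20/20 as failure.

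**A mixed population is intended.** The aim covers suspected or confirmed cases, so the overall comparison answers the stated question. That does not explain why the confirmed-case comparison behind section 1.5 is absent.

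**The rationale runs the other way.** One might infer that the protocol holds infection to cause the dysbiosis under study. Sections 1.1 B and 1.2 mainly argue that dysbiosis drives severity; infection is said to impair the gut barrier. The case for adjustment rests on prognosis, and Day 0 stool samples and ANCOVA on the pretreatment value already absorb some baseline difference.

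**The omission is not fully proven.** The factor list opens non-exhaustively, MaAsLin2 can take confounders, laboratory data may be retrieved, and the appendices holding the forms are not available. So it cannot be said that final results go uncollected. It can be said that neither document names the result as a factor, a covariate or the basis of an analysis set.

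**Conclusion.** The concern holds as a loss of precision and interpretability. The trial counts on confirmed cases for its power, yet its allocation, models and analysis sets name no infection variable. Over 40 to 70 infected among 100, the gap in infected share has an SD of about 9-10 points and reaches 20 points or more in about 4-7% of trials.

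The stated 20 per group is an expectation at 40% positivity. If the total is left to chance at that rate, both arms reach 20 in 31% of trials and both reach 16 in 82%. These shortfall figures are a worst case and fade quickly as more participants enter already positive.

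The figures assume arms of exactly 50 in step 2, minimization factors unrelated to infection, and no dropout. The precision to be gained depends on how strongly infection predicts each outcome, which the documents do not quantify. For a feasibility and exploratory trial this is a worthwhile, inexpensive improvement, and it does not invalidate the design.

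**What to change.** 1. Record in Castor, for every participant, the final result of the test sampled before randomization. A result that arrives later is still a baseline variable, provided the specimen was taken before allocation; the date of sampling should be recorded to show this.
2. Name that result as a covariate in the Cox, Fine-and-Gray and mixed models, and in the logistic models where event counts allow. Enter it as a term in the PERMANOVA and MaAsLin2 analyses, since gut microbiota composition is the primary outcome.
3. Pre-specify a confirmed-case analysis by randomized arm beside the intent-to-treat analysis, because section 1.5 is built on confirmed cases. Reword the 20 per group there as an expected number, and state the anticipated mix of positive and pending entrants.
4. Optionally, add positive versus pending at entry to the minimization app. This is worth doing only if a substantial share enters already positive.

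The cost is one database field, one extra parameter per model and some chasing of pending results. Eligibility and the randomized groups do not change. In logistic models for rare events, such as hospitalization, the extra parameter may not be affordable, hence the condition in item 2.
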